9.4.6.3 Prohibited Concomitant Therapies and Drugs

Subjects should not receive other antitumor therapies while on study. If subjects receive additional antitumor therapies, such as chemotherapy, hormone therapy, or immunotherapy, this will be judged to represent evidence of disease recurrence or progression, and study drug will be discontinued. These subjects should complete all off-treatment assessments and continue to be followed for survival in the Posttreatment Phase.

Subjects are prohibited from receiving the following therapies during the Screening and Treatment Phase of this study:

- Antineoplastic systemic chemotherapy or biological therapy
- Immunotherapy not specified in this protocol
- Chemotherapy not specified in this protocol
- Investigational agents other than eribulin mesylate and pembrolizumab
- Radiation therapy
 - Note: Radiation therapy to a symptomatic solitary lesion or to the brain may be considered on an exceptional case-by-case basis after consultation with sponsor. The subject must have clear measurable disease outside the radiated field. Administration of palliative radiation therapy will be considered clinical progression for the purposes of determining PFS.
- Live vaccines within 30 days prior to the first dose of study treatment and while participating in the study. Examples of live vaccines include, but are not limited to, the following: measles, mumps, rubella, varicella/zoster, yellow fever, rabies, BCG, and typhoid vaccine. Seasonal influenza vaccines for injection are generally killed

virus vaccines and are allowed. However, intranasal influenza vaccines (eg, FluMist[®]) are live attenuated vaccines, and are not allowed.

- Systemic glucocorticoids for any purpose other than to modulate symptoms from an AE that is suspected to have an immunologic etiology. The use of physiologic doses of corticosteroids may be approved after consultation with the sponsor.
 - Note: Inhaled steroids are allowed for management of asthma.

For subjects who, in the assessment by the investigator, require the use of any of the aforementioned treatments for clinical management, continuation of the study medication and further participation in the study must be discussed and agreed upon with the sponsor. Subjects may receive other medications that the investigator deems to be medically necessary

There are no prohibited therapies during the Post-Treatment Follow-up Phase.

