6.4.3 Other Efficacy Analyses

The analysis of time to response (TTR) will follow the analysis of PFS. The analysis will be performed in the subjects with confirmed PR/CR by RECIST1.1.

In addition to RECIST1.1 by IIR, tumor assessment data (i.e., ORR, PFS, DOR, and CBR) will be assessed per RECIST1.1 by investigator review and per irRECIST by IIR and investigator review in the sensitivity analysis.

All efficacy analyses will be performed in overall subjects and also for each stratum.

Efficacy outcomes will be further evaluated in the PD-L1 Positive Set. The clinical utility of PD-L1 as a predictive marker in mTNBC subjects who receive eribulin mesylate and pembrolizumab combination treatment will be assessed.

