Censoring rule for PFS by RECIST 1.1

The PFS derivation rules in this SAP follow the sensitivity of analyses described in Food and Drug Administration (FDA) “[Guidance for Industry Clinical Trial Endpoints for the Approval of Cancer Drugs and Biologics \(2007\)](#)”.

Definition of Progression Date: Progression date is assigned to the first time at which radiological progression can be declared.

For progression based on a new lesion, the progression date is the date of the initial detection of the new lesion, if there were multiple new lesions detected, then the earliest date of initial detection will be used.

Table 3 shows the primary censoring rules for the derivation of PFS based upon investigator's tumor assessment.

Censoring rule for irPFS by irRECIST

Definition of progression date by irRECIST (i.e., irPD):

- For the subjects who experience PD by RECIST 1.1 and then confirmed by irPD ($>$ or <28 days) or not confirmed due to any reasons, the first documented PD date by RECIST 1.1 is the date of irPD.
- For the subjects who experience PD by RECIST1.1 and then followed by irCR/irPR/irSD, the first documented progression date is the date of first irPD defined by irRECIST.
- If the subject had new lesion earlier than overall timepoint response of PD in irRECIST, the date of new lesion is not counted as irPD date. (this is different from PD by RECIST 1.1 for which, as soon as subject developed new lesions, subject is considered as PD and PD date is the date of new lesion).

Censoring rule will be same as RECIST1.1 except that for the second rule in [Table 3](#).

“Date of first radiologic PD assessment” means the irPD Date determined as above.

Duration of Response

Duration of Response (DOR) – defined as the time from the date that a confirmed objective response is first documented to the date of PD or death due to any cause for those subjects with a confirmed PR or CR. For subjects who did not experience PD or death by the end of data cut off, the date of last adequate radiologic assessment before missing tumor assessments or new anti-cancer therapy will be used as censoring date.

BOR, PFS and DOR will be defined separately for IIR data and for investigator reviewed data following the same rules.

Table 3. Censoring Rules for Analysis of Progression-Free Survival

No.	Situation	Date of Progression or Censoring	Outcome
1	No baseline or post-baseline tumor assessments	Date of the first dose	Censored

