2	Progression documented between scheduled visits	Date of first radiologic PD assessment	Progressed
3	No progression at the time of data cut-off	Date of last adequate radiologic assessment prior to or on date of data cut-off	Censored
4	New anticancer treatment started	Date of last adequate radiologic assessment prior to or on date of new anticancer treatment	Censored
5	Death before first PD assessment	Date of death	Progressed
6	Death between adequate assessment visits*	Date of death	Progressed
7	Death or progression after two or more missed visit**	Date of last adequate radiologic assessment before missed tumor assessments	Censored

CR = complete response, PD = progressive disease, PR = partial response, SD = stable disease,

* Adequate tumor assessment is a radiologic assessment of CR, PR, SD, non-CR/non-PD or PD as determined by investigators.

New anticancer treatment includes palliative radiotherapy. Any tumor assessments after new anticancer treatment started will be removed in the definition of PFS.

** More than two missed visits is defined if the duration between the last tumor assessment (including NE) and death or PD is longer than 126 days (18 weeks) or 168 days (e.g. 24 weeks) for subjects on the every 9 or 12 week scanning schedule in this study:

The priority of the censoring rules is as follows:

1. If the subject had PD or death, the following sequence will be applied:

- If a subject did not have baseline tumor assessment (No. 1), the subject will be censored on date of the first dose. However, if the subject did not have baseline tumor assessment and died within 126 days (18 weeks) after the first dose and did not receive new anticancer treatment, the date of death will be the PFS event date (not censored).
- If a subject had new anticancer treatment before PD or death (No. 4), the subject will be censored on the date of the last adequate tumor assessment prior to or on the date of new anticancer treatment.
- If a subject missed two assessments before PD or death (No. 7), the subject will be censored on the date of the last adequate tumor assessment before PD or death. Note that if a subject is censored by both this criterion and the anticancer treatment criteria, the earliest

censoring date will be used.

- Otherwise, if a subject had an event (No. 2, No. 5, or No. 6), the earliest event date will be used.

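### The protocol counts palliative radiotherapy as a PFS event; the SAP censors it in every planned PFS analysis and does not record the departure

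*SAP*

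**What the plan says.** Protocol 9.4.6.3 prohibits radiotherapy during treatment, with an exception for a symptomatic solitary lesion or the brain, which "may be considered on an exceptional case-by-case basis after consultation with sponsor". The same note then gives the consequence for the endpoint: "Administration of palliative radiation therapy will be considered clinical progression for the purposes of determining PFS".

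SAP Section 8 derives PFS differently. Progression is radiologic: "Progression date is assigned to the first time at which radiological progression can be declared". The footnote to Table 3 says "New anticancer treatment includes palliative radiotherapy. Any tumor assessments after new anticancer treatment started will be removed in the definition of PFS". Row 4 of that table gives the outcome for new anticancer treatment as censored, dated at the last adequate scan on or before its start. The priority rules confirm that this overrides a later event: "If a subject had new anticancer treatment before PD or death (No. 4), the subject will be censored".

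Elsewhere, Protocol 8.2 and 9.7.1.1 set the main PFS as RECIST 1.1 by independent imaging review (IIR). Protocol 9.7.1.6.2 leaves the PFS censoring rules to the SAP, and Protocol 9.7.5 requires departures from the protocol's analysis plan to be documented in the SAP.

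**The concern.** The two documents give opposite outcomes for the same subject and the same endpoint. Someone who reads 9.4.6.3 would take radiotherapy before radiologic progression as a PFS event. The reported PFS would treat that subject as censored, and nothing in the SAP would alert the reader.

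Direction matters as well as consistency. Radiotherapy to a symptomatic lesion is plausibly a sign that treatment is failing. Kaplan-Meier assumes that censored subjects have the same outlook as those still at risk. If irradiated subjects do worse, censoring them pushes the PFS curve upward. In a single-arm study there is no concurrent control in which the same bias could offset it.

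The point concerns radiotherapy in PFS only. It claims no conflict for duration of response or for other new anticancer therapy.

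**Working it through.** **1. The two rules for a subject irradiated before radiologic progression**

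| | Protocol 9.4.6.3 | SAP Section 8 |
|---|---|---|
| Class of radiotherapy | Clinical progression | New anticancer treatment |
| PFS outcome | Event | Censored |
| Date used | None stated | Last adequate scan on or before radiotherapy |
| Progression or death afterwards | Irrelevant, event already counted | Not counted |

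Radiotherapy after documented progression is not affected: the earlier progression stays as the event.

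**2. Does any planned PFS analysis follow 9.4.6.3?**

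- IIR and investigator PFS: no. "BOR, PFS and DOR will be defined separately for IIR data and for investigator reviewed data following the same rules".
- irRECIST PFS: no. "Censoring rule will be same as RECIST1.1 except that for the second rule in" Table 3, which only redefines the progression date in row 2. Row 4 is unchanged.
- Sensitivity analyses in SAP 6.4.3: no. Tumour data "will be assessed per RECIST1.1 by investigator review and per irRECIST by IIR and investigator review in the sensitivity analysis", which varies the reader and the response criteria but not the censoring.

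**3. Size**

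The plan states no figure that depends on this rule, so there is none to reproduce. The following is an illustration.

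Inputs from the documents: about 170 subjects (Protocol 9.3), at least 100 evaluable in Stratum 2, scans every 9 weeks (Protocol 9.5.1.4.1), PFS reported at 6, 9 and 12 months (SAP 6.4.2).

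Assumed, because the documents give no values: 2%, 3% or 5% irradiated before radiologic progression (0.02 × 170 = 3.4 to 0.05 × 170 = 8.5, so 3 to 9 subjects); exponential PFS with median 3, 4 or 6 months; event dated at the start of radiotherapy under the protocol rule; cutoff at 104 weeks.

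*Closed form, radiotherapy independent of progression.* With progression hazard λ, radiotherapy hazard μ and share f = μ/(λ+μ), the median with radiotherapy as an event is (1 − f) times the median with radiotherapy censored. For an illustrative median of 126 days and f = 5%: 0.95 × 126 = 119.7 days. PFS at 182.6 days is 0.5^(182.6/126) = 0.366 if censored and 0.5^(182.6/119.7) = 0.347 if an event, a gap of 1.9 points.

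*Simulation with 9-week scans,* 3,000 trials per scenario, n = 170. Case A puts radiotherapy at true progression; case B puts it at a random time before detection. Six months is 26.1 weeks, just before the week-27 scan, so the last scan is at week 18. With no radiotherapy and every event found at a scan, PFS would be 0.5^(18/13.05) = 0.384 for a 3-month median, 0.5^(18/17.4) = 0.488 for 4 months and 0.5^(18/26.1) = 0.620 for 6 months. The simulated values lie around these.

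6-month PFS, protocol rule / SAP rule:

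| Case, median | 2% | 3% | 5% |
|---|---|---|---|
| A, 3 mo | 0.381 / 0.390 | 0.381 / 0.394 | 0.378 / 0.399 |
| A, 4 mo | 0.485 / 0.493 | 0.484 / 0.497 | 0.480 / 0.502 |
| A, 6 mo | 0.619 / 0.626 | 0.616 / 0.628 | 0.614 / 0.634 |
| B, 3 mo | 0.379 / 0.388 | 0.376 / 0.389 | 0.370 / 0.393 |
| B, 4 mo | 0.481 / 0.491 | 0.478 / 0.493 | 0.473 / 0.498 |
| B, 6 mo | 0.614 / 0.624 | 0.611 / 0.627 | 0.602 / 0.629 |

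Before rounding, the gaps are 0.78–1.04 points at 2%, 1.15–1.58 at 3% and 1.93–2.67 at 5%, with simulation error of at most 0.02 points. The 95% half-width is 1.96 × √(p(1−p)/n): for p = 0.381, 1.96 × √(0.381 × 0.619/170) = 7.3 points; for p = 0.485, 7.5 points.

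Other time points and Stratum 2 (2,000 trials per scenario at shares 2% and 5%, except the 27.5-week row, which comes from the 3,000-trial set at 2% to 5%):

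| Setting | Gap (points) | Half-width (points) |
|---|---|---|
| n = 170, 27.5 weeks (after the week-27 scan) | 0.56–2.19 | 6.3–7.5 |
| n = 170, 9 months | 0.43–2.08 | 5.3–7.3 |
| n = 170, 12 months | 0.31–1.93 | 4.3–6.9 |
| n = 100, 6 months | 0.76–2.66 | 9.5–9.8 |

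The typical median PFS moved by one scan in 2 of the 18 scenarios (3 medians × 3 shares × 2 cases), both in case A at 5%. The SAP rule gave the higher PFS throughout.

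**The case against.** The best reply is that the protocol never intended a clinical event in its analysed PFS. Its objectives and statistical sections point to documented progression per RECIST 1.1 by IIR. The contrary sentence sits in the prohibited-medication section, and 9.7.1.6.2 hands censoring to the SAP. The SAP names radiotherapy openly and cites an FDA guidance as the source of its PFS rules. On this reading the SAP settles an inconsistency within the protocol, and the effect is small.

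Part of this stands. The protocol is itself unclear. Protocol 9.7.1.1.3 allows exceptions to RECIST 1.1 where otherwise specified, but that clause may refer only to irRECIST. The informative nature of the censoring is an inference. The separate programming specifications and table shells are not available, so the finding covers the protocol and SAP only. A rule that counts radiotherapy as an event while new systemic therapy stays censored is also a mixed rule, although the radiotherapy sentence is the only one in 9.4.6.3 that names PFS.

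The rest does not remove the problem. The sentence states how PFS is to be determined. Leaving censoring rules to the SAP does not plainly cover turning a stated event into a censoring. Citing a guidance may justify the choice, but it does not disclose that the choice reverses the protocol. One can argue that 9.4.6.3 lies outside the analysis plan to which 9.7.5 applies. But if only radiologic PFS was meant, the sentence has no effect in any planned analysis, which is itself a reason to reconcile the texts.

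**Conclusion.** The concern holds. The protocol and SAP treat palliative radiotherapy before radiologic progression in opposite ways for PFS, no analysis in either document follows the protocol sentence, and the SAP does not acknowledge the difference. The SAP rule is explicit, so the reported result is determined. What is missing is disclosure and a check of its influence.

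The size is unknown and probably small, since the protocol treats such radiotherapy as exceptional. With an assumed share of 2% to 5%, medians of 3 to 6 months and exponential PFS, the SAP rule raises 6-month PFS by 0.78 to 2.67 points, well inside the sampling half-width but always in the favourable direction. PFS is a descriptive secondary endpoint, so alpha, power and the ORR conclusions are untouched. This should be corrected, but it does not threaten the primary result.

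**What to change.** Reconcile the sentence in Protocol 9.4.6.3 with SAP Table 3, its footnote and the priority rules. State in the SAP which handling is primary for PFS by IIR. If censoring stays primary, record and explain the departure from 9.4.6.3.

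Prespecify one PFS sensitivity analysis under the other rule. If censoring stays primary, that analysis counts palliative radiotherapy before radiologic progression as an event on its start date. The date convention has to be written down, because the protocol gives none. Duration of response and the rule for other new anticancer therapy can stay as they are.

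The cost is a few sentences in the SAP and one extra PFS derivation. Radiotherapy start dates are already needed for the present censoring rule, so there are no new data to collect and no change in sample size.

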9.5.1.4.1 TUMOR RESPONSE ASSESSMENT

Tumor assessments will be performed using RECIST 1.1 ([Appendix 3](#)). Investigator assessment will be performed at each assessment time point and entered onto the CRFs. Copies of all tumor assessment scans will be sent to an independent core laboratory designated by the sponsor for efficacy assessment. Note: As of Protocol Amendment 05, tumor assessment scans will no longer be sent to an independent imaging core laboratory.

Tumor assessments will be carried out during the Pretreatment Phase and then every 9 weeks \pm 1 week (or sooner if there is evidence of progressive disease) after the start of study treatment. Computed tomography/MRI scans of chest, abdomen, and pelvis and of other known sites of disease will be obtained at Screening (within 28 days prior to Cycle 1/Day 1), at all tumor assessment time points, and as indicated clinically. Color photographs containing a mm scale must be taken of all skin lesions being used as target lesions. Historical standard of care scans that are performed with scanning parameters consistent with the requirements for this protocol within 28 days prior to dosing are acceptable.

The CT scan should be a diagnostic quality spiral or multidetector CT with oral and iodinated IV contrast, and the MRI scan should be performed with IV gadolinium chelate. Scans of the abdomen, pelvis, and other areas of the body may be done with MRI instead of CT, but evaluation of the chest must be done with CT. If iodinated IV contrast is contraindicated, the chest evaluation should be done with non-contrast CT, and the abdomen and pelvis evaluation should be performed using either CT with oral contrast (without IV contrast) or MRI with gadolinium chelate IV contrast (the latter is preferred). Spiral/multidetector CT should be performed with a 5-mm contiguous slice reconstruction algorithm. If body MRI scans are performed, contiguous slices of 5 mm are also recommended.

Low-dose non-contrast CT transmission scans from a positron emission tomography-CT (PET-CT) combination scanner are not acceptable. Ultrasound should not be used for radiographic tumor assessment. Chest disease may not be followed using chest x-ray.

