A brain scan (CT with contrast or MRI pre- and post-gadolinium) must be performed at Screening (within 28 days prior to Cycle 1/Day 1), to assess potential CNS disease and/or metastases. For subjects with previously treated eligible brain metastases, a brain scan will be performed at tumor assessment time points, if clinically indicated.

The tumor assessment schedule should not be affected by interruptions in study treatment.

The same method of assessment used at Screening must be used at all time points.

Throughout the study it is critical that the same imaging methodology be applied and contrast be consistently provided unless IV contrast becomes medically contraindicated during the course of treatment or the dose of contrast needs to be adjusted based on the subject's health status.

Bone scans will be performed at Screening, every 27 weeks, or sooner if clinically indicated, and at confirmation of CR. A bone scan (⁹⁹m-technetium polyphosphonate scintigraphy, whole body bone MRI, or ¹⁸F-NaF-PET) to assess bone metastases will be performed within 6 weeks prior to C1D1 (historical scans are acceptable) and then every 27 weeks (within that 27th week) from C1D1, or sooner if clinically indicated. In subjects whose body CT/MRI scans indicate CR has been achieved, a bone scan will be required at confirmation of CR to exclude new bone metastases. The same methodology and acquisition techniques used at screening should be used throughout the study to ensure comparability. Lesions detected on bone scans must be followed with cross-sectional imaging.

Tumor response will be confirmed by a second examination performed no less than 4 weeks after the first observation of response. Best overall response (BOR) of stable disease requires at least 1 posttreatment assessment that meets the SD criteria at least 8 weeks after the start of treatment.

In subjects who discontinue study therapy without documented disease progression, every effort should be made to continue monitoring their disease status by radiologic imaging every 9 weeks \pm 1 week during Year 1, and every 9 to 12 weeks \pm 1 week thereafter according to standard of care, until (1) the start of new anticancer treatment, (2) disease progression (3) death, or (4) the end of the study, whichever occurs first.

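### The day limit behind the PFS missed-visit rule leaves no room for the ±1 week scan windows, so a progression found after only one missed scan can be censored

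*SAP*

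**What the plan says.** SAP Section 8 describes one censoring situation in three ways.

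- Table 3 row 7: "Death or progression after two or more missed visit". The subject is censored at the last adequate scan before the gap.
- Footnote ** to that row measures a gap: "More than two missed visits is defined if the duration between the last tumor assessment (including NE) and death or PD". The situation applies once that gap, in days, "is longer than 126 days (18 weeks) or 168 days (e.g. 24 weeks". The two limits apply to 9- and 12-weekly scanning.
- The priority list under the table: "If a subject missed two assessments before PD or death (No. 7". This step comes before the event rows (2, 5 and 6), so once the limit is passed a documented progression no longer counts as an event.

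The same list, in its exception for subjects with no baseline scan, counts from a different starting point: "died within 126 days (18 weeks) after the first dose".

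Protocol Section 9.5.1.4.1 sets the scan calendar: "Tumor assessments will be carried out during the Pretreatment Phase and then every 9 weeks", with one week allowed either side, from the start of treatment. It adds: "The tumor assessment schedule should not be affected by interruptions in study treatment". Baseline scans "will be obtained at Screening (within 28 days prior to Cycle 1/Day 1". For subjects off treatment without progression, scanning after Year 1 is every 9 to 12 weeks by local standard of care, again ±1 week.

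SAP Section 6.4.2 reports PFS as a Kaplan-Meier median and as rates at 6, 9 and 12 months.

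**The concern.** The three labels (two or more, more than two, two) do not agree, and only the day limit can be programmed. That limit fits none of the labels cleanly. It equals two scan intervals on nominal dates, which is the gap after one missed scan. A shift of a single day within the permitted windows then turns a progression that followed one missed scan into a censored observation, although row 7 is meant for two or more.

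Censoring such a subject at the earlier scan removes a real event and tends to raise the later part of the PFS curve. No planned analysis would show this. Section 8 applies the same rules to independent and investigator review and carries them into irRECIST PFS with a change to row 2 only. The sensitivity analyses in Section 6.4.3 vary the reader and the response criteria, not the missed-visit rule.

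**Working it through.** **Inputs.** Intervals of 9 and 12 weeks, a window of ±7 days per scan and a baseline scan up to 28 days before first dose (Protocol 9.5.1.4.1). Limits of 126 and 168 days (SAP Table 3, footnote **).

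**The plan's figures.** 2 × 9 × 7 = 126 and 2 × 12 × 7 = 168. Both are reproduced exactly, with a window allowance of zero.

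**Gap from last scan to progression scan after k missed scans.** (k + 1) × interval × 7 days, ±14 days (last scan up to 7 days early or late, progression scan likewise).

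| Missed scans | 9-weekly (days) | 12-weekly (days) |
|---|---|---|
| 0 | 49 to 77 | 70 to 98 |
| 1 | 112 to 140 | 154 to 182 |
| 2 | 175 to 203 | 238 to 266 |

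The limits fall in the middle of the one-missed row. Example: scan at Week 8 (Week 9 less 1), Week 18 missed, progression seen at Week 28 (Week 27 plus 1). The gap is 20 weeks, or 140 days, so the subject is censored after one missed scan.

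**Share censored after one missed scan.** With both scan dates uniform over ±7 whole days (assumption) there are 15 × 15 = 225 pairs. In 15 the shifts are equal, and half of the other 210 give a gap above the limit: 105/225 = 47%. With only ±3 days used it is 21/49 = 43%, and with ±1 day 3/9 = 33%. On exactly nominal dates the gap equals the limit, is not longer than it, and the event is kept.

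**With a 14-day allowance.** At 140 and 182 days no in-window progression after one missed scan exceeds the limit (maxima 140 and 182), and every one after two missed scans does (minima 175 and 238).

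**If the baseline scan counts as the last assessment.** Week 9 missed, progression at Week 18 ± 7 days, baseline 1 to 28 days before first dose: the gap is 119 + 1 = 120 to 133 + 28 = 161 days. Of 28 × 15 = 420 combinations, 28 are at or below 126 days, so 392/420 = 93% would be censored (uniform dates assumed). Counted from first dose the gap is 119 to 133 days, and none exceeds 140.

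**Trial-level size, without the baseline reading.** Simulation assumptions: 170 treated, exponential PFS, 15% of the PFS hazard from death without progression, 9-weekly scans, 730 days of follow-up, 400 runs per case. The comparison rule counts scan windows actually missed.

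| Median PFS (months) | Scans missed | Progressions after exactly one missed scan | Of these, censored at >126 days | Change in 12-month PFS (points) |
|---|---|---|---|---|
| 3 | 5% | 9.1 | 4.4 | +0.19 |
| 3 | 10% | 16.9 | 8.1 | +0.36 |
| 4 | 5% | 9.3 | 4.5 | +0.39 |
| 4 | 10% | 16.8 | 8.1 | +0.71 |
| 6 | 5% | 9.0 | 4.3 | +0.56 |
| 6 | 10% | 16.5 | 8.1 | +1.10 |

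The 9-month changes are +0.20 to +1.01 points. Standard errors of the 9- and 12-month rates are 2.28 to 3.91 points. The median moves by -1 to +5 days. With 0% or 30% of the hazard from death, the 9- and 12-month changes range from +0.15 to +1.35 points. The 6-month rate was not examined.

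**The case against.** The strongest reply is that the footnote is the definition and the row text only a label. The rule can be programmed without doubt, and 126 versus 140 days is a choice between conventions. On this view the simulation shows a difference between two rules, not a bias against true PFS.

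That reply only partly stands. The simulation did use a missed-window rule, not true progression times, as its reference. But dating a progression at the late scan already places it after the true event, and censoring it at the earlier scan pushes the later rates further up. The window allowance therefore moves the rule towards its own label and not away from the truth.

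Other points carry weight. The 5 to 10% missed-scan rate has no source in the documents. Scans may be done early when progression is suspected, which shortens gaps and which the simulation does not model. Non-evaluable scans count as assessments. All of these keep the effect small. Limits of 140 and 182 days alone would also not serve subjects scanned every 10 or 11 weeks after Year 1, or those changing schedule.

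A reader might infer that one missed Week 9 scan almost always leads to censoring. That needs the baseline scan to count as the last tumor assessment. The footnote does not say so: it refers to assessments that can be non-evaluable, the adequate-assessment note lists response categories that a baseline scan does not have, and the no-baseline exception counts from first dose. The text leaves this open, so the 93% is conditional and does not enter the conclusion.

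**Conclusion.** The point holds as a minor defect of definition. The limits of 126 and 168 days contain no window allowance, so a progression after one missed scan can be censored although row 7 asks for two or more. This follows from the two documents alone. The 47% (33% with ±1 day) rests on an assumed spread of scan dates. The rise of about 0.2 to 1.1 points in the 9- and 12-month PFS rates rests on the simulation assumptions and on 5 to 10% of scans being missed.

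Two stronger inferences are not supported. It is not true that every progression after one missed scan is censored: gaps up to and including the limit are kept. Nor does this threaten the trial's conclusions: PFS is secondary, single-arm and descriptive, the shift is well inside sampling error, and the primary ORR does not use the rule.

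**What to change.** Use the single label of two or more missed visits in row 7, footnote ** and the priority list. Define it as a gap longer than twice the subject's applicable scan interval plus 2 weeks, measured from the later of first dose and last tumor assessment:

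- 9-weekly: 126 + 14 = 140 days
- 10-weekly: 140 + 14 = 154 days
- 11-weekly: 154 + 14 = 168 days
- 12-weekly: 168 + 14 = 182 days
- at a change of schedule: the two intervals spanned plus 14 days, for example 63 + 84 + 14 = 161 for a move from 9- to 12-weekly.

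The limit must follow the schedule in force. Applying 182 days to a 9-weekly subject would miss some gaps after two missed scans, which start at 175 days. Starting from the later of the two dates also settles the baseline question. Alternatively, count scheduled scan windows that closed without an assessment, which is exact for deaths as well. Keep 126/168 days as a sensitivity analysis.

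The cost is SAP wording, a few constants, the start date of the gap and slightly more programming, with no protocol change and no new data. One downside remains under the day limit. On 9-weekly scanning the second missed window closes at a gap of 126 to 140 days, so a few deaths just after it are kept as events (0.01 to 0.04 per trial in the simulation).
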